# 2. Glossary of terms and abbreviations

APR Annual Progress Report

CRF Case Report Form

DRS Decision Regret Score
GCP Good Clinical Practice

GDPR General Data Protection Regulation

MCS Mental Component Summary

MHRA Medicines and Healthcare products Regulatory Agency

Participant An individual who takes part in a clinical trial

PCS Physical component survey
PCTU Pragmatic Clinical Trials Unit
PIS Participant Information Sheet
REC Research Ethics Committee
SAP Statistical Analysis Plan

SF-12 Short form-12

SOP Standard Operating Procedure

QALY Quality Adjusted Life Year

OSIRIS Protocol v2.0 20.11.2023 Page **6** of **46** 

# 4. Synopsis

	Cluster randomised trial on optimising shared decision-				
Full title	making for high-risk major surgery				
Short title and / or acronym	OSIRIS Trial				
Sponsor	Queen Mary University of London				
Device Classification	Class I				
Medical condition or disease					
under investigation	Surgical patients				
Study design and methodology	National multi-centre cluster randomised trial				
Planned number of clusters	40 (approx. 20 hospitals in the usual care arm and 20				
(hospitals)	hospitals in the intervention arm)				
Planned number of participants	600 in total				
Objectives	To evaluate the clinical effectiveness of a decision support intervention in a cluster randomised trial to improve shared decision making for high-risk surgical patients and their doctors				
Inclusion and exclusion criteria for hospitals	Hospitals providing services for high-risk patients in one or more of the following surgical procedures:  • Elective colorectal bowel resection for cancer,  • Hip-replacement or  • Abdominal aortic aneurysm surgery				
Inclusion and exclusion criteria for participants	
 
Patients contemplating elective colorectal bowel resection for cancer, hip-replacement or abdominal aortic aneurysm surgery
 
Age 60 years and over
 
Age-adjusted Charlson co-morbidity index ≥3
 
Exclusion criteria
 
Inability or refusal to provide informed consent
 
Patients expected to die within 12 months of treatment
 
				
Investigational device	Decision aid				
Treatment duration	Length of the surgical consultation (approximately 15-20 minutes)				
Follow-up duration	180 days from patient visit at which surgery decision is made (index decision making episode)				
Total duration for participants	180 days				
Planned enrolment period	12 months				
Planned duration of investigation	24 months				
End of trial definition	The end of the study is defined as the point when the last patient has completed the 180-day follow-up				

### 5. Introduction

Far from being replaced by new drug therapies, surgical treatments are offered to more patients than ever before. This is a particular concern for the 250,000 NHS patients at high risk of post-operative complications who undergo major surgery each year [1]. These patients are older, and usually have chronic disease. Even when surgery and anaesthesia are straightforward, one in three high-risk patients still develops medical complications in the days following surgery [2]. These complications delay recovery, with prolonged hospital stays and poor functional independence once patients return home. Critically, many high-risk surgical patients never recover from these adverse effects, suffering significant reductions in long-term quality of life and survival [2, 3]. For many, surgery is not the successful treatment they hoped for. Feelings of guilt or regret over the decision to undergo surgery are commonplace [4]. Doctors recognise the urgent need to improve decision making for this patient group but clearly feel ill-equipped to tackle this [5]. This problem is becoming more frequent as surgical treatments are offered to more patients living with chronic disease.

Understandably, surgeons and anaesthetists are focused on safe and effective care during surgery and the days that follow. High-risk patients are most likely to experience life-threatening complications during this period and receive good information about these short-term risks. Meanwhile, information on long-term outcomes is mostly focused on the index disease that surgery is treating e.g. osteoarthritis, bowel cancer or vascular disease. The benefits of surgical treatment may, however, be self-limiting for high-risk patients who experience deterioration in other aspects of their health. Few doctors have the breadth of expertise, or the detailed knowledge needed to forecast every likely long-term outcome for complex surgical patients with multiple co-morbid diseases, whilst patients often have unrealistic expectations of what surgery can achieve. High-risk patients frequently consent to surgery unaware that poor long-term outcomes may completely negate the potential benefits.

We know patient opinions about high-burden treatments vary widely, and that quality of life is valued above quantity of life in some situations [6-9]. Patients in their last year of life are more likely to accept treatments with a high risk of death but refuse those with a high risk of functional impairment [10]. Shared decision making is clearly a very different challenge for the high-risk surgical patient but there is little evidence to inform this process. It is likely that doctors and patients use different values to inform their decisions, leading to differences in forecasting and mismatch in expectations. The

OSIRIS Protocol v2.0 20.11.2023 Page **10** of **46** 

information patients seek before surgery may not be the information they need to make an informed decision they do not regret. Most NHS hospitals now offer a consultant delivered pre-operative risk assessment service with access to various predictive tests. Currently these clinics only focus on short term (<30 days) risks of surgery [11], but they are also ideally suited to offer counselling and advice to complex patients about the long-term risks of major surgery and how these may be mitigated.

As the standard of decision making for the high-risk surgical patient falls further behind that of surgery in general, there is a growing urgency to address this problem. UK General Medical Council guidelines specify shared decision making as the standard of care for consent for surgery, but most doctors do not feel prepared to meet this standard for complex high-risk surgical patients for whom the risks and benefits of surgery may be uncertain [5]. There is a need for a user-friendly decision support intervention, which highlights the key information high-risk patients, and their doctors require as they contemplate major surgery, delivering this information in an accurate and easily understood way to ensure patients make an informed decision they do not regret. However, this technology might have adverse effects such as causing greater confusion or stress amongst patients contemplating surgery. It is imperative that the effectiveness of any decision support tool is assessed thoroughly before wider dissemination. The OSIRIS team has developed decision support intervention software to provide an individualised forecast of key long-term outcomes for each high-risk surgical patient, to help doctors and patients understand the long-term implications of decisions about surgery for each patient. We now need to evaluate the clinical effectiveness of this intervention.

#### 6. Trial objectives

The primary trial objective is to determine the clinical and cost-effectiveness of a decision support intervention relative to best standard of care for shared decision making in reducing decision regret after surgery whilst not adversely affecting mental health-related quality of life at 180 days after the index decision making episode at which the decision to proceed or not proceed with surgery is made.

#### 6.1 Primary outcome measure

The co-primary outcome measures are as follows:

OSIRIS Protocol v2.0 20.11.2023 Page **11** of **46** 

• Patients' decision regret at 180 days after the index decision making episode using the Decision Regret Scale (DRS) [12]. The DRS is an easily administered 5-item Likert-type measure written to assess regret or remorse following a medical decision. To help others interpret the score more readily with other scales ranging from 0 to 100, scores are converted to a 0-100 scale by subtracting 1 from each item then multiply by 25. To obtain a final score, the items are summed and averaged. A score of 0 means no regret; a score of 100 means high regret. It has been validated as a useful indicator of health care decision regret at a given point in time [12]. DRS manual:

https://decisionaid.ohri.ca/docs/develop/User\_manuals/UM\_Regret\_Scale.pdf

Patients' mental-health related quality of life at 180 days after the index decision making episode using the Mental Component Summary (MCS) score of the Short Form-12 (SF-12) Health Survey with UK derived weightings [13, 14]. The SF-12 Health Survey is a generic health-related quality-of-life instrument. It was originally developed in 1994 as a shorter alternative (12 items) to the widely used Short-Form 36 Health Survey, for studies in which a 36-item form was too long. The items of the SF-12 were selected to reproduce the two summary measures, Physical Component Summary (PCS) and Mental Component Summary (MCS), of the SF-36. The SF-12 mental component summary (MCS-12) scoring method proposed by Ware et al will be used, [15] this assumes that each item contributes to both physical component summary and that these two measures are uncorrelated. Validation studies have shown the SF-12 yielded acceptable results for detecting both active and recent depressive disorders in general population samples. MCS-12 use norm-based scoring, where the mental summary measures have a mean of 50 and an SD of 10 in the general population and scores greater than 50 reflect better mental health status than the general population and scores lower than 50 worse mental health.

## 6.2 Secondary outcome measures

- The SF-12 PCS Score at 180 days after the index decision making episode.
- Patient satisfaction with decision making using the Shared Decision-Making Questionnaire within 48 hours of decision making [16].
- Generic health-related quality of life utility, derived from participants' EQ-5D-5L questionnaire responses at 180 days after the index decision making episode.

OSIRIS Protocol v2.0 20.11.2023 Page **12** of **46** 

#### 6.3 Estimand framework

Inference on the primary outcomes is complicated by the potential occurrence of intercurrent events. The estimand framework is used to describe how these events are dealt with. Details of the analytical strategy for each intercurrent event type are presented in Appendix 1. The estimand of primary interest for both primary outcomes is the participant—average (rather than cluster-average) treatment effect.

## 6.3.1 Primary estimand for Decision Regret Scale

In patients aged ≥60 years with age-adjusted Charlson co-morbidity index ≥3 who contemplate elective surgery for colorectal resection for cancer, total hip replacement or abdominal aortic aneurysm, what is the difference in mean decision regret score (as measured with the DRS and death defined as a score of 50) between the decision support intervention followed by any subsequent medication or procedure (as needed) compared with Best Standard of Care for shared decision making followed by any subsequent medication or procedure (as needed), at 180 days from the index decision making episode, regardless of whether surgery (if chosen) has been delayed or taken place and any deaths that may have occurred. The objective is to demonstrate statistical superiority of the decision support intervention compared with Best Standard Care for this estimand.

## 6.3.2 Primary estimand for Mental Component Summary

In patients aged ≥60 years with age-adjusted Charlson co-morbidity index ≥3 who contemplate elective surgery for colorectal resection for cancer, total hip replacement or abdominal aortic aneurysm, what is the difference in mean mental-health related quality of life score (as measured with the MCS of the Short Form-12 Health Survey and death defined as a score of 50) between the decision support intervention followed by any subsequent medication or procedure (as needed) compared with best standard of care for shared decision making followed by any subsequent medication or procedure (as needed), at 180 days from the index decision making episode, regardless of whether surgery (if chosen) has been delayed or taken place and any deaths that may have occurred. The objective is to demonstrate non-inferiority of the decision support intervention compared with best standard care for this estimand.

OSIRIS Protocol v2.0 20.11.2023 Page **13** of **46** 

# 7. Trial methodology

#### 7.1 Study design

Multi-centre, open, cluster randomised controlled trial.

## 7.2 Study setting

The study will take place in the UK across 40 NHS hospitals (approximately 20 hospitals in the intervention arm and 20 hospitals in the usual care arm) and there may be multiple hospitals from single Trust included in the study. Hospitals are the units of randomisation (clusters).

#### 7.3 Assessment and management of risk

Risks: There is a small risk that patients may find it distressing to be provided with information, which may indicate poor expected outcomes in the following months and years. Additionally, it is expected that the use of the decision aid will lengthen the consultation itself (this will be measured as part of the study).

Benefits: There is a potential benefit of increased patient involvement in decision making resulting in reduced decision regret after surgery, and improved satisfaction with the decision making process. Enhanced patient participation in decision-making could also potentially improve mental quality of life outcomes. This device is categorised as a Class I.

### 8. Patient recruitment

## 8.1 Target accrual

600 patients across 40 hospitals.

#### 8.2 Participant identification and screening

Potential participants will be screened by the direct care team at the site having been identified from pre-admission clinic lists, operating theatre lists and by communication with the relevant nursing and medical staff. In this trial, the member of the research team conducting the screening activity can be considered part of the direct care team in accordance with local hospital policy.

All study related correspondence should be documented in the medical record as per GCP and local hospital guidelines. If participants are approached by a research nurse, eligibility will need to be confirmed by the surgeon or delegated clinician prior to enrolment. All patients that undergo screening and meet the inclusion criteria will be recorded on the paper screening log stored in the investigator site file. Only anonymised screening data will be collected by the central trial coordinating team for publication purposes. Once the patient has been enrolled, they will also be recorded on the study enrolment log together with their trial ID.

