#### 12.2 Randomisation method

Clusters (hospitals) will be randomised to either intervention or control with a 1:1 allocation ratio. Random permuted blocks randomisation with block sizes of m=4 and 2 will be used. This is a restricted randomisation scheme without stratification. A manual randomisation system (see 12.3) will be used and no adaptive element is envisaged.

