## 12.3 Randomisation procedure

The code creating the randomisation list will be prepared by the trial statistician. The live allocation list will be generated by an independent statistician from within the Pragmatic Clinical Trials Unit (PCTU). Manual randomisation will be carried out remotely by the PCTU. A member of the research team who is un-blinded will be authorised to request randomisation of a cluster via email to the named independent statistician who will return the allocation also via email within one working day. PCTU will designate a standby who can provide allocations should the independent statistician be unavailable. Further details will be explained the Data Management plan which will be agreed and signed off between the trial study team and PCTU.

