#### 12.10 Minimising bias

It is not possible to conceal treatment allocation from all staff in trials of this type. Patients and staff delivering the intervention will be unblinded. However, by randomising

OSIRIS Protocol v2.0 20.11.2023 Page **23** of **46** 

at the level of hospitals, we will eliminate the possibility of between group/surgeon contamination. All doctors in both groups will experience similar levels of additional observation. It is understood that the standard of shared decision making may improve for all patients regardless of study group allocation due to the raised awareness and scrutiny of trial participation. The trial management group and the trial steering committee will not see results broken down by treatment arm during the trial. Final analysis will occur once all follow up data is collected, the final statistical analysis plan has been signed off and data cleaning has occurred.

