#### 14.7 Administration of investigational device

The device will be used by surgeons, anaesthetists and nurses participating in the clinical trial and recorded in the site delegation log. It will be used during clinical consultation with patients regarding proposed surgery.

OSIRIS Protocol v2.0 20.11.2023 Page **26** of **46** 

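### Section 8.2 does not require consecutive approach or recruiters unaware of allocation, so patient selection can differ by arm in this open cluster trial, with decision regret the more exposed outcome

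*Protocol*

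**What the plan says.** Section 7.1 describes a "Multi-centre, open, cluster randomised controlled trial", and section 12.2 states that "Clusters (hospitals) will be randomised to either intervention or control with a 1:1 allocation ratio". Under section 12.3 the request for a hospital's arm goes to an independent statistician "who will return the allocation also via email within one working day". Section 12.10 adds that "Patients and staff delivering the intervention will be unblinded".

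The care team at each hospital screens patients (section 8.2). The sources are pre-admission clinic lists, operating theatre lists, and contact with ward and clinic staff: "by communication with the relevant nursing and medical staff". Where a research nurse makes the approach, "eligibility will need to be confirmed by the surgeon or delegated clinician prior to enrolment". The inclusion criteria in 11.2 are objective (procedure, age, Charlson score). One exclusion, expected death within 12 months, is the treating clinician's judgement (11.3). Site staff take consent (section 9).

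In intervention hospitals the same professions deliver the intervention: "The device will be used by surgeons, anaesthetists and nurses participating in the clinical trial" (14.7). They must be trained before they receive a password (14.6). Control hospitals get no training and no change to care (12.7).

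The schedule in 12.1 collects SF-12 and EQ-5D-5L before the index decision and DRS only at 180 days. Section 17.4 adjusts both outcomes for age, procedure and Charlson score, and MCS also for its baseline value.

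**The concern.** Randomising hospitals makes hospitals comparable. Patients are comparable only if the way they enter the trial does not depend on the arm, and two common protections are absent here. Section 8.2 does not say that eligible patients are approached consecutively, and no section provides recruiters unaware of allocation or identifies patients before their hospital is allocated.

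The protocol also contains features that could make selection differ between arms. Section 7.3 accepts that the forecast may distress some patients and that the aid is expected to lengthen the consultation. Section 14.5 makes non-use in a consented intervention patient a protocol deviation. None of these considerations applies in a control hospital. Section 12.10 deals with contamination, similar observation of doctors in both arms, and committees not seeing results by arm. It does not deal with differential recruitment.

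Intention-to-treat does not help, because 17.3 starts from patients already recruited and consented. The intervention is declared effective only if both co-primary tests succeed. If MCS is truly equal between arms (about 91% power), the DRS test largely decides the verdict. If DRS truly benefits (99.8% power), the MCS test does.

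**Working it through.** **Order of events.** No section says outright that recruitment follows allocation. The inference rests on four points:
- allocation comes back within one working day (12.3);
- training precedes device access (14.6);
- control sites receive no training (12.7);
- staff delivering the intervention are unblinded (12.10).

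No section has patients identified before their hospital is randomised.

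**Inputs from section 17.1.** ICC 0.01; 40 hospitals with 15 patients each; 20% loss to follow-up; MCS SD 11 and margin 3.5; DRS SD 16 and difference 7.5; one-sided 2.5% for MCS, two-sided 5% for DRS.

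**The plan's own figures reproduce** (normal approximation).
- MCS per arm: 2 × (1.960 + 1.282)² × 11² / 3.5², rounded up to 208, so 416 in total.
- Analysed per hospital: 15 × 0.8 = 12. Design effect: 1 + (12 − 1) × 0.01 = 1.11.
- 416 × 1.11 = 461.8. With 460/40 = 11.5 per hospital, 416 × 1.105 = 459.7. The stated figure is 460.
- 460/0.8 = 575, rounded up to 40 × 15 = 600. Analysed: 480, or 240 per arm.
- DRS power at 480 analysed: 99.8%, as stated. Joint power: 0.900 + 0.998 − 1 = 0.898, as stated.

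All of these assume exchangeable arms.

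**Standard errors.** SE = SD × √(2/240 × 1.11) = SD × 0.0962.
- DRS: 16 × 0.0962 = 1.54.
- MCS: 11 × 0.0962 = 1.06.

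**Effect of a residual shift b** (points left after covariate adjustment). The size of b is an assumption.
- DRS two-sided error with no true effect: Φ(b/1.54 − 1.96) + Φ(−b/1.54 − 1.96).
- False MCS non-inferiority at a true deficit of 3.5, shift favouring the intervention: Φ(b/1.06 − 1.96).
- MCS power with no true difference, shift against the intervention: Φ((3.5 − b)/1.06 − 1.96).

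| b (points) | DRS two-sided error | False MCS non-inferiority | MCS power, unfavourable shift |
|---|---|---|---|
| 0 | 5% | 2.5% | 91% |
| 0.5 | 6.2% | 6.8% | 81% |
| 1 | 10.0% | 15.5% | 66% |
| 2 | 25.5% | 47% | 29% |

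For DRS at b = 1 in favour of the intervention, 9.5 of the 10.0 percentage points are false claims of benefit, against 2.5 with no shift. An unfavourable DRS shift costs little power at the planned 7.5 points: b = 2 gives Φ(5.5/1.54 − 1.96), about 95%.

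**Scale of b.** In SD units, 0.5 to 2 points is 0.03 to 0.13 for DRS (0.5/16 to 2/16) and 0.05 to 0.18 for MCS (0.5/11 to 2/11). If 10% of one arm were replaced by patients 1 SD different, the shift before adjustment would be 0.10 × 16 = 1.6 DRS points or 0.10 × 11 = 1.1 MCS points.

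**The case against.** Several points on the other side stand.

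- **Hand-picking is not shown.** A reader might infer that staff choose whom they like. Clinic and theatre lists are named first, the inclusion criteria are objective, and 8.2 logs every screened patient who meets them. Section 9 also logs reasons for patients consented but not entered. The protocol gives no size for the eligible pool, so the room for choice is unknown. What remains is that a patient never put forward for screening need not appear on the log, and that 8.2 gives publication as the purpose of central collection, with no comparison by arm.
- **Surgeon sign-off is not the main route.** It applies only when a research nurse makes the approach, a delegate may give it, and it is a check against fixed criteria. Section 21.1 forbids enrolling ineligible patients. It shows that clinicians are involved in entry. It does not show that they choose among eligible patients.
- **The direction is unknown.** Less anxious patients might favour the intervention, while undecided patients might regret more and count against it. The documents support neither reading.
- **The two outcomes are not equally exposed.** Baseline MCS should absorb much of any selection on mood, so the MCS figures hold only for a shift that survives that adjustment.

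None of this supplies consecutive approach, recruiters unaware of allocation, or a baseline measure in the DRS model.

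**Conclusion.** The point stands as a design risk. Section 8.2 leaves a route by which the arms can differ in who is recruited, and no other section closes it. DRS is the more exposed outcome. Bias has not been demonstrated, and the documents would not support saying that it has.

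The size rests on an assumed residual shift. At 1 point favouring the intervention, the DRS two-sided error goes from 5% to about 10% (about 25% at 2 points) and false MCS non-inferiority at the margin from 2.5% to about 15%. At 1 point against, MCS power falls from 91% to about 66%. These figures also assume that recruitment follows allocation, the SDs and ICC of 17.1, the full 480 analysed, and a normal approximation. A larger sample would not remove the bias.

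**What to change.** 1. **Section 17.4.** Add baseline MCS and baseline EQ-5D-5L utility as covariates in the DRS model. Both are already collected before the index decision, so this is essentially free. The EQ-5D-5L to use is the baseline one; the post-clinic form records predicted quality of life.
2. **Section 8.2.** State that, in both arms, patients meeting the age, procedure and Charlson criteria are approached consecutively in clinic-list order. Patients notified by staff join the same list without priority. Every eligible patient not approached or not enrolled is logged with a reason. Dropping staff contact altogether is not advised, since it could miss patients before the index decision.
3. **Oversight.** Have the independent PCTU statistician compare screened, approached and consented numbers, and baseline characteristics, by arm.

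The cost is some extra screening and logging at 40 hospitals and less freedom for sites in choosing whom to approach. Recruiters would still know the arm, and consent given with knowledge of allocation would remain a residual risk that should be acknowledged in 12.10.
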